4.3 JUSTIFICATION FOR DOSE

The chosen duration and frequency of application are based on established dermatological guidelines for similar treatments. This regimen is believed to provide sufficient exposure to light therapy to elicit measurable changes in skin condition without overexposure or causing undue stress to the skin. The dose is designed to balance efficacy with safety, ensuring that participants experience the full benefits of the treatment without significant risk of adverse effects.

4.4 END OF STUDY DEFINITION

The study concludes after 12 weeks, with the final collection of data, photos, and participant feedback. Adherence to ethical principles and participant safety is paramount throughout the trial process. Should any significant adverse events arise, the study may be adjusted or halted to prioritize participant well-being.

5 STUDY POPULATION

5.1 INCLUSION CRITERIA

To be eligible to participate in this study, an individual must meet all of the following criteria:

- Female
- Aged 25-55 years.
- Willing to follow the study protocols.
- Self-reported issues with at least two of the following:
 - Fine lines
 - Wrinkles
 - Hyperpigmentation
 - Dark spots
 - Reduced elasticity
- Self-report concerns with at least one of the following:
 - Crepey skin on the neck and chest
 - Sun damage on neck and chest
- Willing to avoid introducing any new products, prescription medications, or supplements that target skin health during the study period.
- If taking oral supplements or herbal remedies targeted at skin health and appearance, have been consistently taking these for at least 3 months prior to starting the study.
- Is willing to maintain the routine of any oral supplements or herbal remedies targeted at skin health and appearance for the duration of the study.
- Has been using the same skincare routine for at least one month prior to the study start date.
- Willing to maintain the same skincare routine and products throughout the study.
- Willing to avoid direct sun exposure during the study duration
- Willing to wear sunscreen if have to be in the sun

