4.2 SCIENTIFIC RATIONALE FOR STUDY DESIGN

A single-group study is an appropriate design to understand the efficacy and safety of the test product. A design that encompasses 12 weeks is also long enough to determine if the supplement is effective at improving skin health. The data collection intervals for this trial were chosen to minimize the burden on the patients (i.e., not having to travel to a clinic) while still collecting valuable data about the efficacy of the test product over time.

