5.2 EXCLUSION CRITERIA

An individual who meets the following criteria will be excluded from participation in this study:

- Anyone who is extremely satisfied with their skin.
- Anyone who has any chronic health conditions such as oncological (cancer) or psychiatric disorders.
- Anyone who is planning to undergo facial treatments during the study period, including botox, dermal filler, chemical peels, etc. or has experienced any of these treatments in the last 3 months.

- Anyone diagnosed with a skin condition affecting the face and/or neck who has had an active flare-up or breakout within the last year. This includes but is not limited to acne, eczema, psoriasis, rosacea, seborrheic dermatitis, vitiligo, urticaria (hives), warts, atopic dermatitis, melasma, and contact dermatitis.
- Currently using any prescription medications that may affect the skin condition including but not limited to the following:
 - Corticosteroids like prednisone, methylprednisolone
 - Antipsychotics like olanzapine (Zyprexa), risperidone (Risperdal), quetiapine (Seroquel)
 - SSRIs and SNRIs like fluoxetine (Prozac), sertraline (Zoloft), venlafaxine (Effexor)
 - Anticonvulsants like phenytoin (Dilantin), lamotrigine (Lamictal), and carbamazepine (Tegretol)
 - Antihypertensives like lisinopril (Zestril), amlodipine (Norvasc), and propranolol (Inderal)
 - Antithyroid medications like Tapazole (methimazole), Propyl-Thyacil (propylthiouracil)
- Anyone with a history of skin cancer or precancerous skin lesions on the face.
- Anyone who has any known serious allergic reactions that require the use of an Epi-Pen.
- Anyone who has any known allergies to ingredients commonly found in skincare products.
- Anyone who is pregnant, breastfeeding, or trying to conceive
- Anyone who cannot/will not commit to the study protocol.
- Anyone with a history of substance abuse.
- Anyone who has undergone an invasive medical procedure in the three weeks prior to the study or has a procedure planned during the study duration.
- Anyone with a known allergic reaction to aluminum or plastics.
- Anyone who suffers from any photosensitive disorder (sensitization to light).
- Anyone with uncontrolled acne.
- Anyone taking any prescription medication, over-the-counter supplements, or herbal supplements regularly (three or more days per week) that can cause photosensitivity including but not limited to the following:

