 - Antibiotics like tetracyclines (e.g., doxycycline, tetracycline) or sulfonamides (e.g., Bactrim), fluoroquinolones (e.g., ciprofloxacin, levofloxacin)
 - Antifungals like Griseofulvin or Vfend (voriconazole)
 - Diuretics like drugs ending in -thiazides
 - NSAIDs like ibuprofen and Aleve (naproxen)
 - Retinoids or Vitamin A (e.g., Accutane (isotretinoin), (Retin-A) tretinoin)
 - Antidepressants (e.g., SSRIs, Elavil (amitriptyline), Tofranil (imipramine)
 - Antihistamines like Phenergan (promethazine)
 - Antimalarial medications
 - Statins like Lipitor (atorvastatin), Zocor (simvastatin)
 - Antiarrhythmics like Pacerone (amiodarone)
 - St. John's wort
- Anyone who suffers from light-induced headaches or migraines.
- Anyone with a medical history of seizures or epilepsy triggered by light.
- Anyone with an electronic implanted device such as a defibrillator, neurostimulator, pacemaker, or ECG monitor.
- Anyone with a known history of carotid artery disease, stroke or transient ischemic attack (TIA), carotid stenosis, unstable blood pressure, easy fainting, thyroid disease, or of individuals about to undergo surgical procedures in the neck area.
- Anyone who has stopped hormonal birth control in the past month.

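### Section 5.1 asks for only one month of stable skincare before entry, so any benefit still building from a recently started topical product would be counted as mask effect

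*Combined protocol and SAP*

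**What the plan says.** Section 5.1 of the combined protocol and SAP sets two stability windows for background skin products:

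- **Skincare routine:** "Has been using the same skincare routine for at least one month prior to the study start date".
- **Oral supplements and herbal remedies for the skin:** users must "have been consistently taking these for at least 3 months prior to starting the study".

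Two further criteria in 5.1 fix what happens after entry. The participant must be "Willing to maintain the same skincare routine and products throughout the study" and "Willing to avoid introducing any new products, prescription medications, or supplements that target skin health during the study period".

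Section 5.2 excludes botox, filler, peels and similar treatments planned during the study, and anyone who "has experienced any of these treatments in the last 3 months". It also excludes regular users (three or more days a week) of photosensitising prescription medicines and over-the-counter or herbal supplements, naming "Retinoids or Vitamin A (e.g., Accutane (isotretinoin), (Retin-A) tretinoin" among them.

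Section 6.3 states that there is no randomisation or blinding. Section 7 plans repeated-measures tests of change from Baseline and names no covariate or adjustment. The primary endpoint is dermatologist grading of photographs at Baseline and Week 12.

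**The concern.** Topical skincare is the background treatment applied directly to the skin being graded, yet 5.1 gives it a shorter stability window than products taken by mouth for the same purpose. A woman who began a pigment-lightening or firming cream five weeks before the start is eligible and must go on using it. If that cream is still taking effect at Baseline, the rest of its effect falls between the two photographs.

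In a randomised trial such responses would on average be balanced between arms. Here stability before Baseline is the only protection, because the sole contrast is Week 12 against Baseline. The outcomes (fine lines and wrinkles, pigmentation, texture, firmness) are those that such products target, so any remaining effect would tend to favour the mask. Nothing in the plan records when a topical product was started, so the contribution could not be examined afterwards either.

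**Working it through.** **1. The windows.** Taking a month as 52/12 = 4.33 weeks, the topical window is about 4.3 weeks and the oral window 3 × 4.33 = 13 weeks. The gap is a topical started between about 4 and 13 weeks before entry.

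**2. Do other criteria close the gap?**
- The bar on new skin-targeting products applies during the study period, not before it.
- The requirement to keep the routine unchanged means that the recent product continues.
- The retinoid entry belongs to an exclusion worded for photosensitising medicines and supplements. Cosmetic topicals for pigment, firming or texture are not named.
- The exclusion of prescription medicines that may affect the skin does not cover non-prescription cosmetics.

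The gap stays open for ordinary cosmetic topicals.

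**3. The plan's own figures.** Section 5.4 gives a sample size of 38 without significance level, power, effect size, SD or dropout. There is no calculation to reproduce, and what follows is illustration.

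**4. Model.** Assume a one-sample t-test on the change score, two-sided 5%, n = 38, true mask effect zero, SD of change 1 apart from the topical effect. A share q of participants has a remaining topical gain g (in SD) after Baseline.

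- Shift in mean change: q × g
- Variance of change: 1 + q(1 − q)g²
- Standardised effect: d = qg / √(1 + q(1 − q)g²)
- Noncentrality: d√38; critical t on 37 df = 2.026
- Reported probability: upper tail only, that is, significant improvement (nominal 2.5%)

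Neither q nor g is in the documents; both are assumptions.

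| q | g | Shift q × g | d | d√38 | P(significant improvement) |
|---|---|---|---|---|---|
| 10% | 0.25 | 0.025 | 0.0249 | 0.154 | 3.5% |
| 10% | 0.5 | 0.05 | 0.0494 | 0.305 | 4.8% |
| 20% | 0.5 | 0.10 | 0.0981 | 0.605 | 8.5% |
| 30% | 0.5 | 0.15 | 0.1462 | 0.901 | 14.0% |
| 30% | 1.0 | 0.30 | 0.2727 | 1.681 | 37.4% |

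**5. How much response could remain?** Suppose, purely as an assumption, that a topical response builds evenly over 12 weeks. A product started 4 weeks before Baseline then has (12 − 4)/12 = 0.67 of its effect to come. If starts are spread evenly over 4 to 12 weeks before Baseline, the mean start is 8 weeks and the mean remainder is (12 − 8)/12 = 0.33, half as much. Halving a gain of 0.5-1 SD gives 0.25-0.5 SD, for which the table runs from 3.5% to 14.0%.

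**6. Plausibility of the top row.** A remaining gain of 0.5-1 SD at two thirds implies a total product effect of 0.5/0.67 = 0.75 to 1/0.67 = 1.5 SD. Under the same assumed test, 38 participants give 80% power for about 0.47 SD. The 37% figure thus needs both many recent starters and a strong product.

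**The case against.** Much of the case against this point has force.

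- **Time scale.** A reader might infer that the protocol itself takes skin products to act over 12 weeks, from "A design that encompasses 12 weeks is also long enough to determine if the supplement is effective at improving skin health" in section 4.2. That sentence says only that 12 weeks is sufficient follow-up for the test product. It gives no time course for topicals, and section 2.2 lists plumper skin and smoother fine lines as immediate benefits. The even 12-week build-up is therefore an assumption of this review. This objection stands.
- **Comparators.** A reader might also take the 3-month rule for cosmetic treatments as a second stability standard. It is a washout for past treatments, and their waning could bias the other way. Only the oral-product rule is a like-for-like stability window, and even that concerns a different route. This too stands. Differing windows are not in themselves a contradiction; the point is that the shorter one is unexplained.
- **Gains before Baseline.** Improvement in the first month or more of use is already in the Baseline grade. Only what remains can bias the result.
- **Size.** The share of recent starters has no source in the documents, and the lower rows of the table lie close to 2.5%.
- **Root cause.** The lack of a control group is the larger problem, and changing one window leaves the contrast uncontrolled. True, but within the chosen design the window is the available protection.
- **Practicality.** A virtual, self-reporting sample may find it hard to tell anti-ageing products from basic moisturisers. That is a reason for a carefully worded screening question and for the fallback below.

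None of these explains the one-month window or shows that another rule covers a cosmetic topical started one to three months before entry.

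**Conclusion.** The concern holds in a limited form. Section 5.1 leaves an unexplained gap between one and three months for topical products, and the uncontrolled contrast with Baseline would attribute any benefit still accruing to the mask. The documents do not support the stronger statement that such benefit is present, that it is large, or that most of a recent product's effect falls after Baseline.

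The size cannot be determined. With 10-30% recent starters, the chance of a significant improvement from an inert mask is about 3.5-14% for a remaining gain of 0.25-0.5 SD. It reaches about 37% only at 30% and 1 SD. The nominal value is 2.5%. These figures rest on the assumed shares and gains, a t-test at two-sided 5%, and no mask effect. This is an inexpensive improvement worth making, not a flaw that by itself decides whether the trial can be interpreted.

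**What to change.** In section 5.1, require at least 3 months of stable use before the start for skincare products aimed at ageing, pigmentation, texture or firmness on the face, neck or chest. Keep one month for basic cleansers and moisturisers. This applies the protocol's own oral-product window to topicals. The screening question should list product types, so that participants need not judge a product's purpose themselves.

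If recruitment does not allow this, record the start date of each such product at screening. Then add to section 7 a prespecified repeat of the primary analysis without participants whose product was started less than 3 months before Baseline.

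The cost is one changed criterion, one screening question and somewhat slower recruitment of the 38. Under the fallback there is no loss of recruitment, but the repeat analysis has fewer participants. Either change reduces this source of bias; neither substitutes for a control group.

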5.2 EXCLUSION CRITERIA

An individual who meets the following criteria will be excluded from participation in this study:

- Anyone who is extremely satisfied with their skin.
- Anyone who has any chronic health conditions such as oncological (cancer) or psychiatric disorders.
- Anyone who is planning to undergo facial treatments during the study period, including botox, dermal filler, chemical peels, etc. or has experienced any of these treatments in the last 3 months.

- Anyone diagnosed with a skin condition affecting the face and/or neck who has had an active flare-up or breakout within the last year. This includes but is not limited to acne, eczema, psoriasis, rosacea, seborrheic dermatitis, vitiligo, urticaria (hives), warts, atopic dermatitis, melasma, and contact dermatitis.
- Currently using any prescription medications that may affect the skin condition including but not limited to the following:
 - Corticosteroids like prednisone, methylprednisolone
 - Antipsychotics like olanzapine (Zyprexa), risperidone (Risperdal), quetiapine (Seroquel)
 - SSRIs and SNRIs like fluoxetine (Prozac), sertraline (Zoloft), venlafaxine (Effexor)
 - Anticonvulsants like phenytoin (Dilantin), lamotrigine (Lamictal), and carbamazepine (Tegretol)
 - Antihypertensives like lisinopril (Zestril), amlodipine (Norvasc), and propranolol (Inderal)
 - Antithyroid medications like Tapazole (methimazole), Propyl-Thyacil (propylthiouracil)
- Anyone with a history of skin cancer or precancerous skin lesions on the face.
- Anyone who has any known serious allergic reactions that require the use of an Epi-Pen.
- Anyone who has any known allergies to ingredients commonly found in skincare products.
- Anyone who is pregnant, breastfeeding, or trying to conceive
- Anyone who cannot/will not commit to the study protocol.
- Anyone with a history of substance abuse.
- Anyone who has undergone an invasive medical procedure in the three weeks prior to the study or has a procedure planned during the study duration.
- Anyone with a known allergic reaction to aluminum or plastics.
- Anyone who suffers from any photosensitive disorder (sensitization to light).
- Anyone with uncontrolled acne.
- Anyone taking any prescription medication, over-the-counter supplements, or herbal supplements regularly (three or more days per week) that can cause photosensitivity including but not limited to the following:
 - Antibiotics like tetracyclines (e.g., doxycycline, tetracycline) or sulfonamides (e.g., Bactrim), fluoroquinolones (e.g., ciprofloxacin, levofloxacin)
 - Antifungals like Griseofulvin or Vfend (voriconazole)
 - Diuretics like drugs ending in -thiazides
 - NSAIDs like ibuprofen and Aleve (naproxen)
 - Retinoids or Vitamin A (e.g., Accutane (isotretinoin), (Retin-A) tretinoin)
 - Antidepressants (e.g., SSRIs, Elavil (amitriptyline), Tofranil (imipramine)
 - Antihistamines like Phenergan (promethazine)
 - Antimalarial medications
 - Statins like Lipitor (atorvastatin), Zocor (simvastatin)
 - Antiarrhythmics like Pacerone (amiodarone)
 - St. John's wort
- Anyone who suffers from light-induced headaches or migraines.
- Anyone with a medical history of seizures or epilepsy triggered by light.
- Anyone with an electronic implanted device such as a defibrillator, neurostimulator, pacemaker, or ECG monitor.
- Anyone with a known history of carotid artery disease, stroke or transient ischemic attack (TIA), carotid stenosis, unstable blood pressure, easy fainting, thyroid disease, or of individuals about to undergo surgical procedures in the neck area.
- Anyone who has stopped hormonal birth control in the past month.

5.3 PARTICIPANT COMPENSATION

Participants will each receive a \$125 Visa gift card. Participants will also be permitted to keep the iRESTORE Illumina LED Face Mask and iRESTORE Illumina LED Neck & Chest Mask.

5.4 JUSTIFICATION OF SAMPLE SIZE

A sample size of 38 participants provides a balance between obtaining statistically significant results and maintaining a manageable cohort for detailed analysis and follow-up.

6 STUDY INTERVENTION

6.1 STUDY INTERVENTION

- Participants will be sent one iRESTORE Illumina LED Face Mask and one iRESTORE Illumina LED Neck & Chest Mask.
- Participants will use both products for 10 minutes daily in the evening. For the face mask, Mode 1 should be used for all sessions. The neck and chest mask does not have multiple settings.
- Questionnaires will be completed at Baseline, Week 2, Week 4, Week 6, Week 8, Week 10, and Week 12.
- Photos will be taken at Baseline and Week 12.

6.2 INTERVENTION FORMULATION

N/A

6.3 RANDOMIZATION AND BLINDING

There will be no randomization or blinding in this trial.

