1 PROTOCOL SUMMARY

1.1 SYNOPSIS

Title:	The Effects of an LED Face Mask & Neck and Chest Mask On Skin Health
Study Type:	Single Group, Virtual
Product(s) being tested	The iRESTORE Illumina LED Face Mask and The iRESTORE Illumina LED Neck & Chest Mask
Study Intervention Description:	
This single-group study will involve 38 participants for a total of 12 weeks.
 
Participants will use the test products once daily for 10 minutes in the evening while getting ready for bed.
 
Participants will use Mode 1 only for all sessions of the face mask - the neck and chest mask does not have multiple settings.
 
Participants will complete questionnaires at Baseline, Week 2, Week 4, Week 6, Week 8, Week 10, and Week 12.
 
Participants will also provide photos of their faces at Baseline and Week 12 for dermatologist skin grading.
 
Participants will utilize the test products at home and complete questionnaires online.

Objectives:	
Primary Objective: To examine the effectiveness of the iRESTORE Illumina LED Face Mask and The iRESTORE Illumina LED Neck & Chest Mask in improving skin health outcomes.
 
Secondary Objective: To assess changes in participant perception of skin health.

Endpoints:	
Primary Endpoint: Improvements in skin health parameters will be evaluated by dermatologist grading at Baseline and Week 12.
 
Secondary Endpoint: Participant perceptions of skin health, including plumpness, fine lines and wrinkles, appearance of pigmentation, skin tone and texture, skin redness, firmness, and radiance, and the appearance of crepey skin will be evaluated through subject-specific questionnaires at Baseline, Week 2, Week 4, Week 6, Week 8, Week 10, and Week 12.

Study population	38 female participants aged 25-55
Study Duration:	12 weeks
Description of Sites/Facilities Enrolling Participants:	Virtual

Survey Milestones	Baseline, Week 2, Week 4, Week 6, Week 8, Week 10, and Week 12.
Photo Milestones	Baseline and Week 12

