3 OBJECTIVES AND ENDPOINTS

OBJECTIVES	ENDPOINTS	TIMEPOINTS	ASSESSED BY	JUSTIFICATION FOR ENDPOINTS
Primary Objective : To evaluate changes in overall skin appearance, as measured by dermatologist skin grading.	Improvement in Skin Appearance	Baseline and Week 12	Photographs via Dermatologist Skin Grading	Standardized photographs provide objective data on the changes in skin appearance, specifically targeting wrinkles, fine lines, and other signs of aging.

Secondary Objectives: To assess changes in a range of skin health parameters.	Improvement in skin plumpness, fine lines and wrinkles, pigmentation, tone and texture, redness, firmness, elasticity, radiance, and appearance of crepey skin.	Baseline, Week 2, Week 4, Week 6, Week 8, Week 12	Questionnaires	Self-reported questionnaires provide subjective data on perceived changes in wrinkles and fine lines.
--	---	---	----------------	---

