6.4 PARTICIPANT DISCONTINUATION/WITHDRAWAL FROM THE STUDY

Participants are free to withdraw from participation in the study at any time upon request. An investigator may discontinue or withdraw a participant from the study for the following reasons:

- Pregnancy.
- Significant study intervention non-compliance.
- If any clinical adverse event (AE), laboratory abnormality, or other medical condition or situation occurs such that continued participation in the study would not be in the best interest of the participant.
- Disease progression which requires discontinuation of the study intervention.
- If the participant meets an exclusion criterion (either newly developed or not previously recognized) that precludes further study participation.

- Participants should be withdrawn from study if they start on a new drug or receive antibiotics.

The reason for participant discontinuation or withdrawal from the study will be recorded on a Case Report Form (CRF). Participants who sign the informed consent form but do not receive the study intervention may be replaced. Participants who sign the informed consent form, and receive the study intervention, and subsequently withdraw, or are withdrawn or discontinued from the study, will not be replaced.

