6.5 PHOTO INSTRUCTIONS

Photographs will be taken at Baseline and Week 12 to document changes in appearance.

Face guidelines:

- You will be required to provide photos taken straight on, directly facing the camera, and from the sides at each measurement time point.
- Hair should be tied back.
- The photo should include your full face/head only, with no more than the top of your shoulders visible.
- No cropping: your full face, head, and ears should be included.
- Please use natural light, in a direction that your phone does not cast a shadow on your face when taking the photo, without using the flash.
- Do not use any type of camera filter setting. No makeup should be worn. Neutral facial expression.
- If possible, take your photos in the same location, at the same time of day, and in the same lighting at each check-in.

Neck and Chest Guidelines:

- The photo should be taken straight ahead.
- Please use natural light, in a direction that your phone does not cast a shadow on your face when taking the photo, without using the flash.
- Do not use any type of filter setting. No makeup should be worn. Neutral facial expression.
- If possible, take your photos in the same location, at the same time of day, and in the same lighting at each check-in.

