7 STATISTICAL CONSIDERATIONS

Following data collection and the completion of the trial, the data will be analyzed by Citruslabs to determine the effect of the intervention. Repeated-measure, between time points, statistical tests will be used to examine changes in primary and secondary endpoints versus the Baseline.

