8.7 CONFLICT OF INTEREST POLICY

The independence of this study from any actual or perceived influence is critical. Therefore, any actual conflict of interest of persons who have a role in the design, conduct, analysis, publication, or any aspect of this trial will be disclosed and managed. Furthermore, persons who have a perceived conflict of interest will be required to have such conflicts managed in a way that is appropriate to their participation in the design and conduct of this trial.

The sponsor has a conflict of interest, in that they may benefit financially from the success of the study. To manage the conflict of interest, an independent third party (Citrusabs) will be handling all design and administration of participant-focused materials, all participant recruitment and data gathering, and data analysis.

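### Section 6.3 excludes blinding without exempting the dermatologist, so nothing in the plan stops the grader of the primary endpoint from knowing which photo is Baseline and which is Week 12

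*Combined protocol and SAP*

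**What the plan says.** The Synopsis (Section 1.1) defines the primary endpoint: "Improvements in skin health parameters will be evaluated by dermatologist grading at Baseline and Week 12". Section 3 confirms that the dermatologist works from photographs and justifies the choice by saying "Standardized photographs provide objective data on the changes in skin appearance". Section 7 gives the analysis in one sentence: "Repeated-measure, between time points, statistical tests will be used to examine changes in primary and secondary endpoints versus the Baseline". The comparison is therefore before against after within one group.

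On masking, Section 6.3 consists of a single sentence: "There will be no randomization or blinding in this trial". It names no role to which masking would still apply.

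Section 6.5 tells participants how to take the photos. It does not cover what happens to the files afterwards, such as coding, removal of dates or the order of presentation to the dermatologist. Sections 8.4 (data management) and 8.5 (deviations) add nothing on this. Section 8.7 manages the sponsor's financial interest through a third party that "will be handling all design and administration of participant-focused materials, all participant recruitment and data gathering, and data analysis".

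**The concern.** Grading visible signs of skin ageing from a photograph calls for judgement. A grader who knows that an image was taken after 12 weeks of device use may score it more favourably without intending to. In a controlled trial such a lean would largely cancel if the grader did not know the arm. This trial has no comparator, so a net lean in the grades adds directly to the estimated change from Baseline and cannot be told apart from a device effect. No later analysis can remove it once unmasked grades have been recorded.

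Section 3 treats the photographs as the objective counterpart to the self-report questionnaires. That contrast is not secured if the person scoring the photographs may know the time point. Giving data gathering and analysis to a third party limits the sponsor's influence, but it does not affect what the dermatologist knows when grading.

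**Working it through.** **Step 1. Does any text mask the grader?**

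| Section | Content | Masks the time point? |
|---|---|---|
| 1.1, 1.2, 3 | Dermatologist or expert grading of Baseline and Week 12 photos | No |
| 6.3 | No randomization, no blinding, no exception | No; read literally, excludes it |
| 6.5 | How participants take the photos | No |
| 7 | Change from Baseline, test not named | No |
| 8.4, 8.5 | Data capture, deviations | No |
| 8.7 | Third party gathers and analyses data | No |

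No passage says that the grader will be told the time point, and none prevents it.

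**Step 2. How much could a lean matter?** The plan has no figure to reproduce: Section 5.4 gives 38 participants without alpha, power, SD or effect size, and Section 7 names no test. The rest is an illustration.

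Inputs:
- From the documents: n = 38.
- Assumed: paired t-test, two-sided 5%, true change zero, and a lean d measured in SDs of the paired change.
- Assumed completers of 34 and 30 as alternatives. Section 6.4 says treated participants who "subsequently withdraw, or are withdrawn or discontinued from the study, will not be replaced", so losses reduce n.

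Formula: the test statistic follows a noncentral t distribution with n − 1 degrees of freedom and noncentrality d√n. The chance of a significant result in the improvement direction is P(T > t(0.975, n − 1)).

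For n = 38, √38 = 6.164 and t(0.975, 37) = 2.026. With d = 0.2 the noncentrality is 0.2 × 6.164 = 1.233, and P(T > 2.026) = 22.4%.

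| Lean d | n = 38 | n = 34 (assumed) | n = 30 (assumed) |
|---|---|---|---|
| 0 | 2.5% | 2.5% | 2.5% |
| 0.1 | 8.7% | 8.2% | 7.6% |
| 0.2 | 22.4% | 20.4% | 18.4% |
| 0.3 | 43.7% | 39.7% | 35.5% |
| d at which the chance is 50% | 0.326 | 0.346 | 0.370 |

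A simulation with the Wilcoxon signed-rank test (8,000 trials, normal changes) agrees closely. At d = 0, 0.1, 0.2 and 0.3 it gives 2.5%, 8.9%, 21.8% and 42.3% for n = 38.

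For scale, the change detectable with 80% power at n = 38 is about (1.960 + 0.842)/√38 = 0.45 SD. A lean of 0.2 SD is a little under half of that.

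**The case against.** **Section 6.3 probably concerns treatment allocation.** It sits in the intervention section under a heading that pairs blinding with randomization, and in a one-group device study participants cannot be masked to treatment. This may well be the intent. On that reading the plan is silent on grader masking instead of excluding it, but an unmasked grader still complies with the plan.

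**Silence is not a stated practice.** No passage says the grader will see dates or ordered pairs, and the Manual of Procedures mentioned in Section 8.5 might cover image handling. This limits what can be inferred about how grading will be done. It does not put a safeguard into the protocol.

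**The magnitude is generic.** It is the power curve of a paired t-test with a lean in place of an effect. The test, alpha, SD and lean are all assumed. The Synopsis also speaks of several skin parameters, so a single test may not be the analysis. All of this stands: the figures show sensitivity and do not estimate bias in this trial.

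**Masking would not restore 2.5%.** Matching of the photo setting is only requested where feasible ("If possible, take your photos in the same location, at the same time of day, and in the same lighting at each check-in"), participants are chosen for self-reported skin problems, which invites regression to the mean, and they agree to change their behaviour ("Willing to avoid direct sun exposure during the study duration"). This also stands. If such influences alone moved masked grades by 0.2 SD (assumed), the chance of a significant improvement without any device effect would already be 22.4% at n = 38. A further grader lean of 0.1 SD would take it to the 0.3 SD figure, 43.7%. Masking removes only the grader's part.

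**Other design features could limit discretion.** An anchored scale or several readers could reduce the lean, but readers who know the time point can share the same expectation, and the plan specifies neither.

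**Conclusion.** The concern holds. The only primary endpoint is a judgement-based grade in an uncontrolled before-after comparison, and the plan lets the grader know the time point. This conclusion rests on the text and does not depend on the illustration. Under the stated assumptions, a lean of 0.1 to 0.3 SD gives a false significant improvement in about 9% to 44% of trials with all 38 completing, and in about 8% to 36% with 30. The chance passes one half at about 0.33 SD with 38. Whether a lean would occur, and how large it would be, cannot be learned from the documents. The gap should be closed before any photo is graded, because it is cheap to close then and cannot be repaired afterwards. The lack of a control group remains the larger limit on what the trial can show.

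**What to change.** Reword Section 6.3 to say that participants are not blinded but that photo grading is masked to time point, and add the procedure:

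1. After the last Week 12 photo arrives, the CRO removes dates, file metadata and time-point labels.
2. The CRO gives each image a code and puts the images in random order.
3. The planned dermatologist or dermatologists grade the coded images without knowing the time point.
4. The key is opened only after the grades are locked.

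State the limit in the protocol as well: masking removes directed grader expectation only. It leaves differences in lighting, regression to the mean, and the effects of sun avoidance and sunscreen, so even a masked result would not isolate the device effect.

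Cost: a wording change plus file handling. Assuming one frontal, two side and one neck-and-chest view per time point, based on Section 6.5, there are at most about 4 × 2 × 38 = 304 images to prepare. No participants, visits or graders are added beyond those planned. The drawback is that grading waits for the last Week 12 photo; the documents give no enrolment window from which to judge the delay.
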